12.3 Missed Visits

If a subject misses a scheduled visit, reschedule the subject within the same visit period. Show diligence in trying to schedule the subject for all visits, and document all attempts to contact the subject in the subject's chart. In documentation, include dates, times, method of contact, etc.

If a subject is unable to return for the final study visit, complete the Exit Case Report Form with the appropriate reason for discontinuation. If attempts to contact the subject are unsuccessful, document the date the subject is considered lost to follow-up. Complete the subject's Exit Case Report Form after the last window (Visit 4A) closes, indicating the subject is lost to follow-up.

12.4 Discontinued Subjects

Discontinued subjects withdraw, or are withdrawn from the study after signing consent, and prior to completing all study visits. Subjects signing consent, but withdrawing or withdrawn prior to randomization shall be considered discontinued due to screen failure, and the failed entry criterion documented (eg, inclusion criterion 2, exclusion criterion 5). Refer to Section 10 SUBJECT POPULATION.

Subjects may discontinue study participation at any time and for any reason. Subjects may be discontinued from the study at any time if in the medical opinion of the PI or designated, qualified medical personnel, continued participation poses a health risk to the subject. Subject numbers from discontinued subjects will not be reissued. Discontinued subjects will not be replaced.

12.5 Clinical Trial Termination

The Sponsor reserves the right to close the investigational site or terminate the study in its entirety at any time, for reasonable cause. The Investigator also may terminate the study at his/her site for reasonable cause. Reasons for the closure of an investigational site or termination of a study may include:

- The Investigator fails to comply with the protocol or GCP guidelines
- Safety concerns
- Inadequate recruitment of subjects by the Investigator

If the clinical study is prematurely terminated or suspended, the Sponsor will inform the Investigator and the regulatory authorities (where applicable) of the termination/ suspension

and the reason(s) for the termination/suspension. The Investigator should promptly notify the IEC/IRB of the termination or suspension and of the reasons.

If the Sponsor terminates the study for safety reasons, it will immediately notify the Investigator(s), and provide written instructions for study termination and applicable subject follow-up.

13 DEVICE DEFICIENCIES AND ADVERSE EVENTS

13.1 General Information

Product Complaint

Any oral, electronic, or written communication that alleges deficiencies related to the identity (labeling), quality, durability, reliability, safety, effectiveness, or performance of a marketed product, including failure of the product, labeling or packaging to meet specifications, whether or not the product is related to or caused the alleged deficiency. A complaint may allege that an adverse event or medical device malfunction has occurred.

Device Deficiency

Inadequacy of a medical device with respect to its identity, quality, durability, reliability, safety or performance. Note: This definition includes malfunctions, use errors, and inadequate labeling.

- **Malfunction** is defined as a failure of a device to meet its performance specifications or otherwise perform as intended. Performance specifications include all claims made in the labeling of the device. The intended performance of the device refers to the intended use for which the device is labeled or marketed.
- **Use error** is defined as the act or omission of an act that results in a different medical device response than intended by manufacturer or expected by user.

Examples of device deficiencies include the following:

- Failure to meet product specifications (eg, incorrect IOL power)
- IOL defect
- Broken IOL optic
- Broken IOL haptic
- Scratched IOL optic
- Unsealed device packaging
- Suspect product contamination (IOL)
- Lack of efficacy

Adverse Event (AE)

Any untoward medical occurrence, unintended disease or injury, or untoward clinical signs (including abnormal laboratory findings) in subjects, users or other persons, whether or not related to the medical device.

Serious Adverse Event (SAE)

Adverse event that led to any of the following:

- Death
- A serious deterioration in the health of the subject that either resulted in:
 - a) A life-threatening illness
 - b) Permanent impairment of a body function or permanent damage to a body structure
 - c) A condition necessitating medical or surgical intervention to prevent a) or b)
 - d) A condition that requires hospitalization or significant prolongation of existing hospitalization
 - e) any indirect harm as a consequence of incorrect diagnostic test results when used within manufacturer's instructions for use
- Fetal distress, fetal death, or a congenital abnormality or birth defect

Non-serious adverse event

Any adverse event that does not meet seriousness criteria described above.

Adverse Device Effect (ADE)

Adverse event related to the use of a test article or control article. Note: This definition includes adverse events resulting from insufficient or inadequate instructions for use, deployment, implantation, installation, or operation; any malfunction; and use error or intentional misuse of the test article or control article.

Serious Adverse Device Effect

A serious adverse device effect (SADE) is an ADE that has resulted in any of the consequences characteristic of a SAE.

Serious Public Health Threat

Any event type which results in imminent risk of death, serious deterioration in state of health, or serious illness that requires prompt remedial action. This would include: Events that are of significant and unexpected nature such that they become alarming as a potential public health hazard, eg, human immunodeficiency virus (HIV) or Creutzfeldt-Jacob Disease (CJD).

Figure. 13-1 Categorization of All Adverse Events

[figure not shown]
[figure not shown]

Figure. 13-2 Categorization of All Serious Adverse Events

Specific Events Relevant to this Protocol

In addition to reporting all AEs (serious and non-serious) meeting the definitions, the Investigator must report any occurrence of the following as an SAE:

Cumulative Serious Adverse Events

- Cystoid macular edema
- Hypopyon
- Endophthalmitis
- Lens dislocation
- Pupillary block
- Retinal detachment
- Secondary surgical intervention (excluding posterior capsulotomy)

Persistent Serious Adverse Events

- Corneal stromal edema
- Cystoid macular edema
- Iritis
- Raised IOP requiring treatment

This list is consistent with the categories provided in EN ISO 11979-7:2014. A persistent AE is an AE that is present at the conclusion of a clinical investigation per EN ISO 11979-1:2012. Any other potentially sight-threatening event may also be considered serious based on the judgment of the Investigator and should be reported appropriately as delineated in Section 13.2.

13.2 Recording and Reporting Adverse Events and Device Deficiencies

All AEs (serious and non-serious) and device deficiencies are collected from the time of informed consent in the electronic Case Report Form (eCRF). Any pre-existing medical conditions or signs/symptoms present in a subject prior to the start of the study (ie, before informed consent is signed) are not considered AEs in the study and should be recorded in the Medical History section of the eCRF.

A separate eCRF must be filled out for each event. When possible, signs and symptoms indicating a common underlying pathology should be documented as one comprehensive event.

The site must submit all available information to the Study Sponsor as follows:

- All SAEs must be reported immediately (within 24 hours) of the Investigator's or site's awareness.
- ADEs (related AEs) that do not meet seriousness criteria and Device Deficiencies must be reported within 10 calendar days of the Investigator's or site's awareness.

Please also include a printed copy of the completed Device Deficiency and/or the SAE-ADE eCRF with product returns. Additional relevant information after initial reporting is to be entered into the eCRF as soon as the data become available.

- Document any changes to concomitant medications on the appropriate eCRFs.
- Document all relevant information from Discharge Summary, Autopsy Report, Certificate of Death etc., if applicable, in narrative section of the Adverse Device Effect (for related AEs) and Serious Adverse Event eCRF.

Note: Should the EDC system become non-operational, the site must complete the appropriate paper AE and/or Device Deficiency Form. The completed form is faxed or emailed to the Study Sponsor at [REDACTED] or [REDACTED] within 24 hours of the Investigator's or site's awareness; however, the reported information must be entered into the EDC system once it becomes operational.

Further, depending upon the nature of the AE or device deficiency being reported, the study Sponsor may request copies of applicable portions of the subject's medical records. The Investigator must also report all AEs and device deficiencies according to the requirements of regulatory authorities or IRB/IEC.

Study Sponsor representatives and their contact information are provided in the MOP that accompanies this protocol.

In the very unlikely event of a Serious Public Health Threat being detected, the site must contact the Study Sponsor and the accredited ethics committee immediately.

Intensity and Causality Assessments

For every AE in the study, the Investigator must assess the causality (Related or Not Related to the medical device or study procedure). An assessment of causality will also be performed by study Sponsor utilizing the same definitions, as shown below:

Causality

Related An AE classified as related may be either definitely related or possibly related where a direct cause and effect relationship with the medical device or study procedure has not been demonstrated, but there is a reasonable possibility that the AE was caused by the medical device or study procedure.

Not Related An AE classified as not related may either be definitely unrelated or simply unlikely to be related (ie, there are other more likely causes for the AE).

Where appropriate, the Investigator must assess the intensity (severity) of the AE as mild, moderate, or severe based on medical judgment with consideration of any subjective symptom(s), as defined below:

Intensity (Severity)

Mild An AE is mild if the subject is aware of but can easily tolerate the sign or symptom.

Moderate An AE is moderate if the sign or symptom results in discomfort significant enough to cause interference with the subject's usual activities.

Severe An AE is severe if the sign or symptom is incapacitating and results in the subject's inability to work or engage in their usual activities.

If an AE reported for an Investigator's subject is upgraded to a SAE or if a SAE reported by an Investigator as not related that is subsequently upgraded to be related by the study Sponsor, the Investigator will receive a notification by the study Sponsor.

13.3 Return product analysis

Study Sponsor representatives and their contact information are provided in the MOP that accompanies this protocol.

Alcon Products associated with device deficiencies and/or product related AEs should be returned as specified in the MOP and must include the Complaint # which will be provided by study Sponsor.

13.4 Unmasking of the Study Treatment

Masked information on the identity of the assigned medical device should not be disclosed during the study (see Section 9.2) If the treatment code needs to be broken in the interest of subject safety, the Investigator is encouraged to contact an appropriate study Sponsor representative prior to unmasking the information if there is sufficient time. Dependent upon the individual circumstances (ie, medical emergency), the code may be broken prior to contact with the study Sponsor. The study Sponsor must be informed of all cases in which the code was broken and of the circumstances involved. Additionally, the study Sponsor may be required to unmask the information in order to fulfill expedited regulatory reporting requirements.

13.5 Follow-Up of Subjects with Adverse Events

The Investigator is responsible for adequate and safe medical care of subjects during the study and for ensuring that appropriate medical care and relevant follow-up procedures are maintained after the study.

The Investigator should provide the study Sponsor with any new safety information (which includes new AEs and changes to previously reported AEs) that may affect the safety evaluation of the device. For AEs that are unresolved/ ongoing at time of subject exit from study, any additional information received at follow-up should be documented in the eCRFs up to study completion (ie, database lock).

All complaints received after study completion (ie, after database lock) will be considered and processed as spontaneous (following the post-market vigilance procedures) and should be communicated to the medical device's manufacturer as per local requirements.

The Investigator should report complaints on non-Alcon products directly to the manufacturer as per the manufacturer's instructions or local regulatory requirements.

13.6 Pregnancy in the Clinical Trial

Pregnancy is not reportable as an AE; however, complications may be reportable and will be decided on a case-by-case basis. An Alcon form will be utilized to capture all pregnancy related information until birth of the child.

14 DATA REVIEW AND HANDLING

14.1 Completion of Source Documents and Case Report Forms

The nature and location of all source documents will be identified to ensure that original data required to complete the electronic case report forms (eCRFs) exists and are accessible for verification by the monitor. It is required that the author of each entry in the source documents be identifiable (eg, initials or signature and date). At a minimum, source documents should include the following information for each subject:

- Subject identification (name, date of birth or age, sex)
- Documentation of subject eligibility
- Date of informed consent
- Dates of visits
- Documentation that protocol-specific procedures were performed
- Results of study testing, as required by the protocol
- Test article accountability records
- Documentation of SAEs and other safety parameters (as applicable)
- Records regarding medical histories and the use of concomitant therapies prior to and during the study
- Date of study completion and reason for early discontinuation, if applicable

Note: If electronic source records are maintained, the method of verification must be determined in advance of starting the study.

Direct access to source documentation (medical records) must be allowed for the purpose of verifying that the data recorded on the eCRF are consistent with the original source data. Data reported on the eCRFs shall be derived from source documents and be consistent with these source documents, and any discrepancies shall be explained in writing. Any change or correction to data reported on a source document shall be dated, initialed, and explained if necessary, and shall not obscure the original entry (ie, an audit trail shall be maintained); this applies to both written and electronic changes and corrections. eCRFs shall be signed and dated by the Principal Investigator or his/her authorized designee(s).

14.2 Data Review and Clarifications

Upon completion of the eCRFs, targeted data will be reviewed by the assigned Sponsor global clinical site management (CSM) team for accuracy and completeness. The planned source document verification and overall monitoring activities for this study are outlined in a

separate document, the Protocol Monitoring Plan. Corrections and/or any necessary additions to the data will be applied and if required, queries will be generated. Designated investigative staff are expected to respond to data queries in a timely manner and ensure that the corrections and changes made to the data are reflected in the subjects' source documentation.

Deviations from this protocol, regulatory requirements and GCP must be recorded. An explanation of the deviation should be included, as applicable. In addition, corrective and preventive action should be identified, implemented and documented within the study records. Prior to study start, a plan for data validation will be completed by Alcon clinical data management, and agreed upon by the study clinical manager (CM) and other team members.

Concomitant medications entered into the database will be coded using the WHO Drug Reference List. Medical history and adverse events will be coded using the medical dictionary for regulatory activities (MedDRA) terminology. Upon completion of the study and once the database is declared completed and accurate, the database will be locked and data will be available for data analysis. Any changes to the database after lock will be implemented upon agreement between the Sponsor's clinical trial management, medical safety clinical data management and biostatistics departments, and will be completed following the Sponsor's procedures for changes to a database after database lock.

15 ANALYSIS PLAN

15.1 Subject Evaluability

The final subject evaluability will be determined prior to breaking the code for masked treatment assignment and locking the database. All eyes will be analyzed as implanted.

15.2 Analysis Data Sets

The all-implanted analysis set (AAS) will include all eyes with successful test or control article bilateral implantation.

The best-case analysis set (BAS) will include all eyes successfully implanted with the test or control article that had at least one postoperative visit, and with no macular degeneration at any time, and no major protocol deviations. Subjects who become pregnant at any time during the study will also be excluded from the BAS.

All eyes with attempted test or control article implantation (successful or aborted after contact with the eye) will be considered evaluable for the Safety Set (SS).

The primary analysis set for performance analyses will be the AAS for all performance endpoints, except for binocular defocus and contrast sensitivity for which it will be considered supportive. The BAS will be the primary set for binocular defocus and contrast sensitivity. [REDACTED] The SS will be used for analysis of safety endpoints.

15.3 Demographics and Baseline Characteristics

Summary statistics will be provided for demographic and baseline characteristics by treatment group. Number and percentage will be presented for categorical variables and descriptive statistics including mean, standard deviation, minimum and maximum will be presented for continuous variables.

15.4 Performance Analyses

A total of six hypothesis tests will be conducted to address the primary and secondary objectives of the study.

The primary, second secondary and third secondary will be tests of non-inferiority while the first secondary, fourth secondary and fifth secondary will be tests of superiority. A combination of gate-keeping and Bonferroni adjustment strategies will be employed to

control the overall type I error rate at 0.05. The hypothesis tests and the testing order (multiplicity adjustment) are outlined in Figure 15-1.

15.4.1 Primary Performance

The primary objective is to demonstrate non-inferiority of the TFNT00 IOL to the 839MP IOL in mean photopic binocular uncorrected intermediate (60 cm) visual acuity (UCIVA) at Visit 4A.

15.4.1.1 Statistical Hypotheses

The null and alternative hypotheses for the primary analysis are:

$$H_0: \mu_{\text{TFNT00VA}} - \mu_{\text{839MPVA}} \geq \Delta$$

$$H_A: \mu_{\text{TFNT00VA}} - \mu_{\text{839MPVA}} < \Delta$$

where, Δ refers to the non-inferiority margin, set at 0.1 logMAR, and μ_{TFNT00VA} , μ_{839MPVA} , refer to the mean binocular high contrast UCIVA for the test and control lenses, respectively.

15.4.1.2 Analysis Methods

The primary hypothesis will be tested by generating a two-sided 90% confidence interval using repeated measures analysis of variance at a type I error rate of 5%, 1-sided. Tests at each visit will be reported with Visit 4A (120-180 days) prospectively identified as the primary time point of interest. The upper bound of the two-sided 90% confidence interval will be compared to the margin, 0.1. If the upper bound is less than the margin, the null hypothesis will be rejected and the TFNT00 IOL will be concluded non-inferior to the 839MP IOL for UCIVA.

The two sided 90% confidence intervals will be reported for the difference between the treatment groups at each visit.

15.4.2 Secondary Performance

The first secondary objective is to demonstrate superiority of the TFNT00 IOL to the 839MP IOL in mean photopic binocular uncorrected intermediate (60 cm) visual acuity (UCIVA) at Visit 4A.

The second secondary objective is to demonstrate non-inferiority of the TFNT00 IOL to the 839MP IOL in mean photopic binocular uncorrected distance (4 m) visual acuity (UCDVA) at Visit 4A.

The third secondary objective is to demonstrate non-inferiority of the TNFT00 IOL to the 839MP IOL in mean photopic binocular uncorrected near (40 cm) visual acuity (UCNVA) at Visit 4A.

The fourth secondary objective is to demonstrate superiority of the TFNT00 IOL to the 839MP IOL in mean photopic binocular uncorrected near (40 cm) visual acuity (UCNVA) at Visit 4A.

The fifth secondary objective is to demonstrate superiority of the TFNT00 IOL to the 839MP IOL in mean photopic binocular uncorrected distance (4 m) visual acuity (UCDVA) at Visit 4A.

The sixth secondary objective is to characterize the Binocular Defocus Curve profiles, contrast sensitivity and patient satisfaction with the TFNT00 IOL versus the 839MP IOL at Visit 4A.

The secondary endpoints are UCNVA, UCIVA, UCDVA, Binocular Defocus, Contrast Sensitivity and Patient Satisfaction.

15.4.2.1 Statistical Hypotheses

The null and alternative hypotheses for the first, fourth and fifth secondary analysis are:

$$H_0: \mu_{\text{TFNT00VA}} \geq \mu_{\text{839MPVA}}$$

$$H_A: \mu_{\text{TFNT00VA}} < \mu_{\text{839MPVA}}$$

where μ_{TFNT00VA} , μ_{839MPVA} , refer to the mean binocular high contrast UCIVA, UCNVA or UCDVA for the test and control lenses, respectively.

The null and alternative hypotheses for the second and third secondary analysis are:

$$H_0: \mu_{\text{TFNT00VA}} - \mu_{\text{839MPVA}} \geq \Delta$$

$$H_A: \mu_{\text{TFNT00VA}} - \mu_{\text{839MPVA}} < \Delta$$

where, Δ refers to the non-inferiority margin, set at 0.1 logMAR, and μ_{TFNT00VA} , μ_{839MPVA} , refer to the mean binocular high contrast UCDVA or UCNVA for the test and control lenses, respectively.

15.4.2.2 Analysis Methods

For the superiority hypothesis tests, treatment group comparison for UCIVA will be made and the first secondary objective will be demonstrated if $p < 0.025$ from a repeated measures analysis of variance at a Type I error rate of 2.5%. Tests at each visit will be reported with Visit 4A (120-180 days) prospectively identified as the primary time point of interest. The two-sided 95% confidence intervals will be reported for the difference between treatment groups at each visit. For the fourth and fifth secondary objectives, superiority will be demonstrated if $p < 0.05$ (or $p < 0.025$, depending on the gatekeeping) for UCNVA and UCDVA at Visit 4A (120-180 days), respectively.

For the non-inferiority hypothesis test of UCDVA, the second secondary objective, treatment group comparisons will be tested by generating a two-sided 95% confidence interval from a repeated measures analysis of variance, with site included as a covariate, at a Type I error rate of 2.5%. The variable 'visit' will be entered as a classification variable to avoid assumptions on the shape of the response and least squares means will be used to estimate the treatment effect at each visit with Visit 4A (120-180 days) prospectively identified as the primary point of interest. The upper bound of the two-sided 95% confidence interval will be compared to the margin, 0.1. If the upper bound is less than the margin, the null hypothesis will be rejected and the TNFT00 IOL will be concluded non-inferior to the 839MP IOL for UCDVA. The two-sided 95% confidence intervals will be reported for the difference between the treatment groups at each visit.

For the non-inferiority hypothesis test of UCNVA, the third secondary objective, treatment group comparisons will be tested by generating a two-sided 95% (or 90%, depending on the gatekeeping) confidence interval from a repeated measures analysis of variance, with site included as a covariate, at a Type I error rate of 2.5% (or 5%). The variable 'visit' will be entered as a classification variable to avoid assumptions on the shape of the response and least squares means will be used to estimate the treatment effect at each visit with Visit 4A (120-180 days) prospectively identified as the primary point of interest. The upper bound of the two-sided 95% (or 90%) confidence interval will be compared to the margin, 0.1. If the upper bound is less than the margin, the null hypothesis will be rejected and the TNFT00 IOL will be concluded non-inferior to the 839MP IOL for UCNVA. The two-sided 95% (or 90%) confidence intervals will be reported for the difference between the treatment groups at each visit.

Summaries of logMAR visual acuity will also include two-sided 90% confidence intervals. A composite visual acuity endpoint comprising binocular uncorrected visual acuity at Distance (4 m) and Near (40 cm) will be summarized as a categorical variable with the following

categories: 20/20 or better (≤ 0.04 logMAR), 20/32 or better (≤ 0.14 logMAR) and 20/40 or better (≤ 0.24 logMAR).

Defocus curves will be generated for binocular defocus data, including two-sided 90% confidence intervals, with the amount of defocus along the x-axis and logMAR VA at each defocus point along the y-axis. To examine inter-site variation in outcome, forest plots of near, intermediate and distance visual acuity will be produced by plotting the difference in means and associated standard error for each site.

Contrast Sensitivity will be scored and analyzed per contrast sensitivity unit instructions.

Responses to the satisfaction question will be analyzed as a categorical variable.

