## **4 Effectiveness Analysis Strategy**

A total of six hypothesis tests will be conducted to address the primary and secondary objectives of the study.

The primary (Gate 1 in Figure .4-1) will be a test of non-inferiority, tested at an alpha of 0.05.

The first and second secondary (Gate 2 in Figure .4-1) will be two tests, one of superiority and one of non-inferiority, each tested at an alpha of 0.025 for a family-wise Type I error rate controlled at 0.05. The third secondary will be a test of non-inferiority and the fourth and fifth secondary (Gates 3, 4 and 5 in Figure .4-1) will be tests of superiority at an alpha of 0.05 if both of the first and second secondary null hypotheses are rejected and at an alpha of 0.025

if only one of them is rejected. The sixth secondary objective endpoints [REDACTED] will be summarized descriptively.

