### 4.3.2 Secondary Effectiveness Analyses

#### 4.3.2.1 Visual Acuity

For the superiority hypothesis tests, treatment group comparison for UCIVA will be made and the first secondary objective will be demonstrated if  $p < 0.025$  from a repeated measures analysis of variance. The variable 'visit' will be entered as a classification variable to avoid assumptions on the shape of the response. Tests will be conducted and two-sided 95% confidence intervals for the difference between treatment groups will be generated at each visit with Visit 4A prospectively identified as the primary time point of interest. For the fourth and fifth secondary objectives, superiority will be demonstrated if  $p < 0.05$  (or  $p < 0.025$ , depending on the gatekeeping) for UCNVA and UCDVA at Visit 4A, respectively. SAS pseudo-code for this model will be the same as for the primary effectiveness analysis with, for the first secondary objective, the change to  $\alpha = 0.05$  and for the fourth and fifth secondary objectives the change to  $\alpha = 0.05$  (if only one of the first or second secondary hypotheses is rejected) and  $\alpha = 0.1$  (if both the first and second secondary hypotheses are rejected). The multiple testing strategy is listed in more detail in Section 4.4.

For the non-inferiority hypothesis test of UCDVA, the second secondary objective, treatment group comparisons will be tested by generating a two-sided 95% confidence interval based on least squares means using a repeated measures analysis of variance model. The variable 'visit' will be entered as a classification variable to avoid assumptions on the shape of the response. Two-sided 95% confidence intervals for the difference between treatment groups at each visit will be reported with Visit 4A prospectively identified as the primary time point of interest. The upper bound of the two-sided 95% confidence interval will be compared to the margin, 0.1. If the upper bound is less than the margin, the null hypothesis will be rejected and the TFNT00 IOL will be concluded to be non-inferior to the 839MP IOL for UCDVA. SAS pseudo-code for this model will be the same as for the primary effectiveness analysis with the change to  $\alpha=0.05$ . The multiple testing strategy is listed in more detail in Section 4.4.

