#### 4.4 Multiplicity Strategy

A total of six hypothesis tests will be conducted to address the primary and secondary objectives of the study. All type-I error rates in the following figure are I-sided.

Figure .4-1 Multiple Testing Strategy

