## **7 Sample Size and Power Calculations**

The multiplicity adjustment strategy is outlined in Figure .4-1. Sample size estimations are based on the minimum sample size needed to achieve 90% power for all hypothesis tests. A type I error rate of 2.5%, one-sided, is used for calculations to account for simultaneous testing in Gate 2 (see Figure .4-1).

Assuming a dropout rate of 5%, approximately 160 subjects will be bilaterally implanted in 1:1 allocation ratio (test: control) to achieve at least 152 subjects who complete the study. With 152 subjects (76 per group) there is 98% probability that an upper one-sided 97.5%

confidence limit on the difference (test-control) in visual acuity will be less than 0.1 logMAR, assuming the mean difference of 0.0 logMAR and a common standard deviation of 0.16 logMAR, the maximum observed for binocular uncorrected distance, intermediate and near visual acuity in a previous Alcon study (C-06-40, ReSTOR +3.0 D IOL).

[figure not shown]
Also, with 76 subjects per group, there is more than 90% power to detect a difference of 0.09 logMAR (4.5 letters) between means in a two sample t-test conducted at a 2.5% chance of a Type I error and assuming a standard deviation of 0.16 logMAR for binocular uncorrected distance, intermediate and near visual acuity.

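### Is the superiority rule of p below 0.025 (or 0.05) at odds with the plan's one-sided alpha because the model prints two-sided p-values?

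*Protocol*

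**What the plan says.** For intermediate acuity, Protocol 15.4.2.2 states that "the first secondary objective will be demonstrated if $p < 0.025$ from a repeated measures analysis of variance"; the error rate set for that test is 2.5%. For near acuity it gives this rule, which covers distance acuity as well: "For the fourth and fifth secondary objectives, superiority will be demonstrated if $p < 0.05$ (or $p < 0.025$, depending on the gatekeeping) for UCNVA". SAP 4.3.2.1 repeats both thresholds.

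The sidedness of the tests is dealt with elsewhere:

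- Protocol 15.4.2.1 introduces the superiority hypotheses with "The null and alternative hypotheses for the first, fourth and fifth secondary analysis are". The null is that the TFNT00 mean logMAR is at or above the 839MP mean, and the alternative is that it is below. SAP 4.2.2 has the same pair.
- SAP 4.4: "All type-I error rates in the following figure are I-sided".
- SAP 4, on the first and second secondary tests: "each tested at an alpha of 0.025 for a family-wise Type I error rate controlled at 0.05".
- SAP 4.3.2.1, on the code: "SAS pseudo-code for this model will be the same as for the primary effectiveness analysis with, for the first secondary objective, the change to" an alpha of 0.05. For the fourth and fifth objectives the code alpha is 0.05 or 0.1.
- Protocol 15.10 and SAP 7 base the calculations on a one-sided 2.5% type I error rate and state that, with 76 in each arm, "there is more than 90% power to detect a difference of 0.09 logMAR (4.5 letters) between means in a two sample t-test" with SD 0.16.

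**The concern.** The non-inferiority rules are complete: they name the interval, the bound and the value it is compared with. The superiority rules give only a p threshold. The PROC MIXED pseudo-code in SAP 4.3.1, reused for superiority, requests differences with confidence limits. As general software knowledge (it is not in the documents), the p printed there is two-sided, and the alpha option changes only the interval. The pseudo-code has no step that halves p, and the rule does not mention the sign of the estimate.

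A programmer working from that paragraph alone could therefore compare a two-sided p with 0.025. A printed p between 0.025 and 0.05 would then fail although the 95% interval lies wholly on the TFNT00 side of zero. Read with complete literalness, a small p favouring the control would also pass. The result matters beyond intermediate acuity: under SAP 4.3.2.1, whether the first secondary objective is met helps decide if the third to fifth are tested at 5%, at 2.5% or not at all.

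**Working it through.** **Inputs** (Protocol 15.10, SAP 7): 76 per group, SD 0.16 logMAR, difference 0.09 logMAR, two-sample t-test, one-sided 2.5%.

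**The plan's own figure.**

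- SE = SD × √(2/n) = 0.16 × √(2/76) = 0.02596.
- Noncentrality = 0.09 / 0.02596 = 3.467, with 2 × 76 − 2 = 150 degrees of freedom.
- Power is the probability that a noncentral t exceeds the critical value. At one-sided 0.025 the critical value is 1.976 and power is 93.1% (normal approximation 93.4%).

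The statement of more than 90% is reproduced on the one-sided basis.

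**If an unhalved two-sided p were held to the same threshold.** Two-sided 0.025 puts 0.0125 in the favourable tail, with critical value 2.264.

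| Reading | Smallest observed benefit that succeeds | Power at 0.09 logMAR |
|---|---|---|
| One-sided p < 0.025 | 1.976 × 0.02596 = 0.0513 | 93.1% |
| Two-sided p < 0.025 | 2.264 × 0.02596 = 0.0588 | 88.4% |
| One-sided p < 0.05 | 1.655 × 0.02596 = 0.0430 | 96.5% |
| Two-sided p < 0.05 | 0.0513 (same tail area as the first row) | 93.1% |

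The two readings of the 0.025 threshold give different decisions in 93.1 − 88.4 = 4.7% of trials at a true benefit of 0.09. At true benefits of 0.06 and 0.04, which are illustrative values and not planning assumptions, the figures are 11.2% and 9.6%. With no true difference, the chance of a false favourable claim is 0.025 / 2 = 1.25% instead of 2.5%.

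**Which reading the documents support.** Set each p threshold beside the alpha that SAP 4.3.2.1 gives for the interval in the same analysis.

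| Objective | p threshold | Interval alpha in the code | Ratio |
|---|---|---|---|
| First secondary | 0.025 | 0.05 | 2 |
| Fourth and fifth, one of the first two secondary tests met | 0.025 | 0.05 | 2 |
| Fourth and fifth, both met | 0.05 | 0.1 | 2 |

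A two-sided interval at twice the p threshold matches a one-sided p in every row. A two-sided p would give a ratio of 1 throughout.

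The same paragraph block of Protocol 15.4.2.2 offers a second check. It attaches a 2.5% type I error rate both to the superiority p rule and to the distance non-inferiority test. The latter is decided by the upper bound of a two-sided 95% interval, which is a one-sided 2.5% test. The phrase carries a one-sided meaning where its use can be verified.

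**Direction.** The null includes every case in which TFNT00 is equal to or worse than 839MP. A p-value for that null is small only when the estimate favours TFNT00, so a control-favouring result cannot reject it.

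**The case for a change.** The best argument for acting is that a confirmatory rule should be readable where it stands. The non-inferiority paragraphs meet that standard and the superiority paragraphs do not. Three of the six tests are affected, the result of the first feeds the alpha of later ones, and the cure is one word. If the printed p fell between 0.025 and 0.05, someone could in principle choose a reading after seeing the data.

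Part of this stands. The word is missing beside p in both documents, and the pseudo-code shows no step to a one-sided p. The testing-strategy figures are not reproduced in the available text, so whether they label each test cannot be checked.

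The stronger claim, that the plan contains two conflicting superiority rules, does not stand. The 95% intervals for superiority are to be reported or generated; neither document makes them a success criterion. The disagreement rates above therefore compare the plan's rule under a reading that its own hypotheses exclude with an interval rule that the concern supplies. Nor is there a free choice after the fact: the directional hypotheses, the one-sided error statement and the interval alphas are already written down. The shortfall against the stated power also applies only to the 0.025 threshold, since a two-sided p < 0.05 still has 93.1% power at 0.09.

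**Conclusion.** This is a gap in wording that a competent analyst fills correctly from the rest of the plan. With a one-sided p, the threshold, the intervals, the code alphas and the stated power are mutually consistent, and the power is reproduced at 93.1%.

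If the printed p were used unhalved by mistake, the cost would be 4.7 percentage points of power for the first secondary objective at the planned 0.09 logMAR, with a possible knock-on to the alpha of the third to fifth. The error would be conservative, so it would not inflate the type I error. The primary objective, on which SAP study success depends, is decided by an interval bound and is unaffected.

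The conclusion rests on the plan's SD of 0.16, 76 per group and a t-test in place of the repeated measures model, and on the programmer applying the hypotheses of Protocol 15.4.2.1 and SAP 4.2.2. Adding the word would only restate a sidedness that the plan already determines, so no amendment is needed.
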